## 1.1 Study Rationale

### 1.1.1 Rationale for Investigating First-Line Maintenance Therapy in SCLC

SCLC accounts for 15 to 20% of new cases of lung cancer and is associated with poor outcomes. SCLC is traditionally classified as Limited Stage Disease (LD-SCLC: TNM stages I to IIIB) and Extensive Stage Disease (ED-SCLC: TNM stage IV with distant metastases (M1) including malignant pleural effusions). For LD-SCLC, a combined therapeutic approach of radiotherapy, chemotherapy and (rarely) surgery is used with curative intent[1]. Most patients at diagnosis have ED-SCLC and are treated with four to six cycles of etoposide plus platinum-based therapy (EP), which remains the standard chemotherapy regimen for LD- and ED-SCLC[2]. Overall survival (OS) remains poor with median survival for LD-SCLC at 18 to 30 months[3] and for ED-SCLC in the range of 9 to 12 months[4-7]. Despite high initial response rates, in particular in patients with ED-SCLC, the disease does recur or progress rapidly after completion of chemotherapy, with median PFS of only 2-3 months[7, 8]. A Dutch randomized phase III of patients with ED-SCLC treated with thoracic radiation therapy following EP reported a significant improvement in PFS at 6 months (24% vs 7%, HR 0.73) and a significant improvement in 2 year OS (13% vs 3%, p=0.004) with the addition of thoracic radiation therapy[5]. There are no other established standard of care treatments for subjects with ED-SCLC who complete first line therapy with EP and have achieved stable disease or response. In a phase 3 trial of topotecan versus observation, topotecan did not show an OS prolongation for SCLC patients after completion of EP[8]. Recently, sunitinib showed an improved PFS in a Phase 2 trial of sunitinib vs placebo in SCLC patients after completion of EP[7]. Despite the extensive chemotherapy regimens administered to ED-SCLC patients, approximately 75-90% of patients have persistent intrathoracic disease and though consolidative RT alone to the residual thoracic disease can improve time to progression in the thorax, 2 year OS is still only 13% among patients treated with TRT [5]. This underscores the need for more effective treatment options in this devastating malignancy.

Considering the short median OS for patients who have completed first line platinum-based treatment, as well as the even shorter PFS experienced in this disease, new treatments complementary to SCLC standard first-line platinum-based treatment are required.

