#### **6.5.3.4 Discontinuation Criteria**

Treatment with study therapy should be permanently discontinued for the following:

- Any Grade 2 drug-related uveitis or eye pain or blurred vision that does not respond to topical therapy and does not improve to Grade 1 severity within the re-treatment period OR requires systemic treatment
- Any Grade 3 non-skin, drug-related AE lasting > 7 days, with the following exceptions:
  - Grade 3 drug-related uveitis, pneumonitis, bronchospasm, neurologic toxicity, hypersensitivity reaction, or infusion reaction of any duration requires discontinuation
  - Grade 3 drug-related laboratory abnormalities do not require treatment discontinuation except:
    - ◆ Grade 3 drug-related thrombocytopenia > 7 days or associated with bleeding requires discontinuation
    - ◆ Any drug-related liver function test (LFT) abnormality that meets the following criteria require discontinuation:
      - AST or ALT > 8 x ULN
      - Total bilirubin > 5 x ULN
      - Concurrent AST or ALT > 3 x ULN and total bilirubin > 2 x ULN
- Any Grade 4 drug-related AE or laboratory abnormality, except for the following events which do not require discontinuation:
  - Grade 4 neutropenia  $\leq$  7 days
  - Grade 4 lymphopenia or leukopenia
  - Isolated Grade 4 electrolyte imbalances/abnormalities that are not associated with clinical sequelae and are corrected with supplementation/appropriate management within 72 hours of their onset
  - Grade 4 amylase or lipase abnormalities that are not associated with symptoms or clinical manifestations, or radiographic signs of pancreatitis. It is recommended to consult with the Principal Investigator for Grade 4 amylase or lipase abnormalities
  - For Grade 4 endocrinopathy AEs such as adrenal insufficiency, ACTH deficiency, hyper or hypothyroidosis, or glucose intolerance, which resolve or are adequately controlled with physiologic hormone replacement (steroids, thyroid hormones) or glucose controlling agents, respectively, retreatment can be considered after discussion with the Principal Investigator
- Any dosing interruption lasting > 6 weeks from the last dose with the following exceptions:

- Dosing interruptions to allow for prolonged steroid tapers to manage drug-related AEs are allowed. Prior to re-initiating treatment in a participant with a dosing interruption lasting > 6 weeks from the last dose, the Principal Investigator must be consulted

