## 8 ADVERSE EVENTS

NCI CTCAE Version 4.0 will be utilized for identification and grading of all adverse events.

An Adverse Event (AE) is defined as any new untoward medical occurrence or worsening of a preexisting medical condition in a clinical investigation participant administered study drug and that does not necessarily have a causal relationship with this treatment. An AE can therefore be any unfavorable and unintended sign (such as an abnormal laboratory finding), symptom, or disease temporally associated with the use of study drug, whether or not considered related to the study drug. The causal relationship to study drug is determined by a physician and should be used to assess all adverse events. The causal relationship can be one of the following:

- Unrelated: The Adverse Event is *clearly not related* to the investigational agent(s)
- Unlikely: The Adverse Event is *doubtfully related* to the investigational agent(s)
- Possible: The Adverse Event *may be related* to the investigational agent(s)
- Probable: The Adverse Event is *likely related* to the investigational agent(s)
- Definite: The Adverse Event is *clearly related* to the investigational agent(s)

Adverse events can be spontaneously reported or elicited during open-ended questioning, examination, or evaluation of a participant. (In order to prevent reporting bias, participants should not be questioned regarding the specific occurrence of one or more AEs.)

The study sponsor, Moffitt Cancer Center, will be reporting adverse events to regulatory authorities and ethics committees according to local applicable laws including FDA Code of Federal Regulations 21 CFR Parts 312 and 320. In addition, K08 CA231454-01A1 Grant support will be provided through Moffitt Cancer Center.

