# **9 STATISTICAL CONSIDERATIONS**

## **9.1 Lead in Safety Observation**

We will utilize 6-9 patient safety lead in as described in the Section 4.1 with a dose-limiting toxicity period of 13 weeks. We will initially enroll 6 patients. If 0 or 1 of 6 patients develops unacceptable toxicity, then we will proceed with the study as outlined below (to accrue an additional 46 patients). If 2 patients develop unacceptable toxicity, we will enroll an additional 3 patients to determine the rate of unacceptable toxicity with 9 patients. If 3 or more patients develop unacceptable toxicity during any portion of the safety lead in phase, we will discontinue the study.

Additionally, we will be continually assessing toxicity throughout the study and if at any time 3 of the first 9 patients or greater than 33% of patients experience unacceptable toxicity within the 13 week safety observation period, we will discontinue the study. Following the 13-week safety observation period, toxicity will be assessed on an ongoing basis for all patients prior to each dose of ipilimumab/nivolumab or nivolumab alone until study completion.

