## 9.4 Endpoints

### 9.4.1 Primary Endpoints

**Part I: Safety Run In Phase I:** Unacceptable toxicity status at the end of 13-week safety observation period with unacceptable toxicity defined as:

- Any grade 4 immune related adverse event (irAE),
- Any  $\geq$  grade 3 noninfectious pneumonitis,
- 
- Any grade 3 irAE, excluding pneumonitis, that does not downgrade to grade 2 within 7 days after onset of the event despite optimal medical management including systemic corticosteroids or does not downgrade to  $\leq$  grade 1 or baseline within 14 days,
- Liver transaminase elevation  $> 8 \times$  ULN or total bilirubin  $> 5 \times$  ULN,
- Any  $\geq$  grade 3 non-irAE, except for the following exclusions:
  - grade 3 fatigue lasting  $\leq$  7 days
  - grade 3 endocrine disorder (thyroid, pituitary, and/or adrenal insufficiency) that is managed with or without systemic corticosteroid therapy and/or hormone replacement therapy and the participant is asymptomatic
  - grade 3 infusion-related reaction (first occurrence and in the absence of steroid prophylaxis) that resolves within 6 hours with appropriate clinical management
  - grade 3 or 4 neutropenia that is not associated with fever or systemic infection that improves by at least 1 grade within 3 days.

**Part II: Phase II:** The primary endpoint is 6-month PFS status. PFS is defined as the duration from date of registration to date of first documentation of progression assessed by local investigator or symptomatic deterioration (as defined above) or death due to any cause. Patients last known to be alive without report of progression are censored at date of last disease assessment. For patients with a missing scan (or consecutive missing scans) whose subsequent scan determines progression, the expected date of the first missing scan (as defined by the disease assessment schedule) will be used as the date of progression.

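### The Part I toxicity endpoint counts grade 3 or higher non-immune events and liver elevations whatever their cause, so SCLC progression can inflate the chance of a stop that could not then be attributed to the regimen

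*Combined protocol and SAP*

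**What the plan says.** Section 9.4.1 sets the Part I endpoint as "Unacceptable toxicity status at the end of 13-week safety observation period with unacceptable toxicity defined as" a list of criteria. Three bullets name a kind of event: grade 4 immune-related events, grade 3 or higher noninfectious pneumonitis, and grade 3 immune-related events that do not improve in time. The other two are broader:

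- The non-immune bullet takes in everything at or above "grade 3 non-irAE, except for the following exclusions". The exclusions are short-lived fatigue, managed asymptomatic endocrine disorder, a first brief infusion reaction, and brief uncomplicated neutropenia.
- The liver bullet counts transaminases above 8 x ULN or total bilirubin above 5 x ULN.

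Neither of these two has a causal condition. Section 8 says that an adverse event "does not necessarily have a causal relationship with this treatment". It also provides a five-level causality rating and adds: "The causal relationship to study drug is determined by a physician and should be used to assess all adverse events".

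Section 9.1 gives the rule: 0 or 1 of 6 patients, proceed; 2 of 6, add three patients. Then: "If 3 or more patients develop unacceptable toxicity during any portion of the safety lead in phase, we will discontinue the study". The study also stops at any time if 3 of the first 9 patients, or more than 33% of patients, have unacceptable toxicity within their 13 weeks. Section 4.1 repeats these rules.

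**The concern.** The lead-in is meant to confirm the regimen after thoracic radiotherapy. Section 1.1.1 describes the background course of the disease: "the disease does recur or progress rapidly after completion of chemotherapy, with median PFS of only 2-3 months". A 13-week window is about 3 months, so many patients will progress inside it however safe the regimen is. Dyspnea from tumor growth, a seizure from a new brain metastasis or a death from SCLC meets the non-immune bullet as written. The liver bullet has the same gap. Section 4.4.2 admits patients with liver metastases whose AST and ALT are below 5 x ULN, so hepatic progression could carry one of them past 8 x ULN.

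The omission does not look deliberate. The individual delay and discontinuation rules in Sections 6.5.3.2 and 6.5.3.4 are largely framed around drug-related events. Section 6.5.3.4 uses the same liver thresholds (8 x and 5 x ULN) but only for drug-related abnormalities. The rule that closes the whole study leaves the qualifier out. With 6 to 9 patients, one or two misattributed events can decide whether the study continues.

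**Working it through.** **The plan's own figures.** The documents give no acceptable toxicity rate and no operating characteristics for the lead-in, so there is no lead-in figure to reproduce. The one stated design figure is the Section 9.2 Simon design (stop at 4 or fewer of 18, reject at 18 or more of 52). It reproduces: exact type I error is 0.0494 at 24% and power is 0.9035 at 44%. The present point does not depend on it.

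**Inputs.**
- Decision rule: Sections 4.1 and 9.1.
- q, the true probability of treatment-related unacceptable toxicity per patient: illustrated at 10%, 20% and 30%. Section 1.1.3 reports 30% drug-related grade 3-4 events with this drug combination, a broader category than the endpoint.
- b, the probability of a counted event due to disease within the window: not in the documents. Assuming exponential times, median PFS of 3 months gives 1 - 0.5^(3/3) = 50% progressed by 3 months. A median of 2 months gives 1 - 0.5^(3/2) = 65%. The 24% 6-month PFS in Section 9.2 gives 1 - 0.24^(1/2) = 51%. If half progress, and 10-40% of those have a grade 3 or higher event (an assumption), then b = 0.5 x 0.10 to 0.5 x 0.40 = 5% to 20%.

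**Formulas.** With q and b independent, the counted rate is p = 1 - (1 - q)(1 - b). For the 6+3 rule,

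P(stop) = P(X6 >= 3) + P(X6 = 2) x [1 - (1 - p)^3], with X6 ~ Bin(6, p).

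**Two worked cases.**
- q = 10%, b = 0: p = 0.10, and 0.0159 + 0.0984 x 0.271 = 0.043.
- q = 10%, b = 10%: p = 1 - 0.9 x 0.9 = 0.19, and 0.0870 + 0.2331 x 0.4686 = 0.196.

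**P(stop), 6+3 rule.**

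| q | b = 0 | 5% | 10% | 15% | 20% |
|---|---|---|---|---|---|
| 0 | 0 | 0.7% | 4.3% | 11.5% | 21.9% |
| 10% | 4.3% | 10.6% | 19.6% | 30.3% | 41.8% |
| 20% | 21.9% | 31.6% | 41.8% | 51.9% | 61.4% |
| 30% | 46.9% | 55.5% | 63.6% | 70.9% | 77.4% |

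**Expansion.** At q = 10%, the chance of exactly 2 of 6 rises from 9.8% to 23.3% at b = 10% and 31.6% at b = 20%.

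**Other stopping rules.** For 3 or more of the first 9, P(X9 >= 3) at q = 10% is 5.3% with b = 0, 23.6% with b = 10% and 48.3% with b = 20%. At q = 20% it is 26.2%, 48.3% and 68.6%. With the >33% rule then run to 52 patients by exact recursion, background alone (q = 0) stops the study with probability 0.9%, 5.7%, 16.0% and 31.8% for b = 5%, 10%, 15% and 20%.

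**The nearest figure in the documents.** Section 1.1.4 reports 7.2% grade 3 or higher toxic effects in the arm without thoracic radiotherapy (time window not given). Using it as b, background alone gives 1.8%; q = 10% goes from 4.3% to 14.3%, and q = 20% from 21.9% to 36.0%.

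**The case against.** The strongest reply has four parts.

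*The text implies attribution.* The endpoint is called toxicity, Section 9.1 speaks of a dose-limiting toxicity period, and Section 8 says that causality is to be used in assessing all events. Section 8.1 ties SAE reporting of endpoint components to relatedness. None of this filters the count. Section 9.4.1 defines the term by its list, the Section 8.1 text governs reporting, and the monitoring committee's judgement in Section 4.1 is an additional ground for stopping.

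*Progression is not a grade 3 event.* This stands. Entry requires ECOG 0-1 and ongoing response or stable disease. It excludes supplemental oxygen, and previous brain metastases must be treated, asymptomatic and stable. A reader might infer from the 2-3 month median PFS that about half of patients would count as toxicity. The documents give no such rate, which is why b is shown as a range.

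*Cause-neutral counting captures radiation toxicity.* This also stands. The Section 8 scale rates only the investigational agents, which Section 6.1 lists as nivolumab and ipilimumab. A filter on drug-relatedness alone would lose events such as severe esophagitis, so the fix must cover radiotherapy.

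*Much of the stopping risk comes from the small sample.* True: at q = 30% the rule stops 46.9% of the time with no background events. At a true 33% rate it passes about 46% of the time. Changing attribution does not alter that.

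The laboratory mismatch is a separate matter. Section 6.5.3.4 says "Grade 3 drug-related laboratory abnormalities do not require treatment discontinuation except" in listed cases, and it also spares grade 4 lymphopenia and leukopenia, whereas Section 9.4.1 spares only neutropenia. A study-level threshold may be stricter than an individual one, and Section 8.3 limits which laboratory results are recorded as events. This calls for reconciliation and is not evidence of a fault in attribution.

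**Conclusion.** The point holds as a fault in the study-level endpoint. Followed as written, the rule counts disease events as regimen toxicity and feeds them into an automatic stop. Over the assumed 5-20% background, the lead-in stop probability for a regimen with 10% true toxicity is roughly 2.5 to 10 times what it would be without those events (10.6/4.3 to 41.8/4.3). At 20% true toxicity it is 1.4 to 2.8 times (31.6/21.9 to 61.4/21.9). These figures rest on the assumed b, on independence of disease and treatment events, and on full follow-up of each patient.

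Two stronger readings are tempting and not supported. The first is that the lead-in cannot answer its safety question. Background events push only toward stopping, so 0 or 1 of 6 remains valid and conservative evidence. The pneumonitis bullet, which addresses the hazard Section 1.4 calls most concerning, and the immune-related bullets are unaffected. The second is that the disease alone is likely to close the study. At b = 5-10% it does so in only 0.7-4.3% of lead-ins; it reaches 21.9% only at b = 20%. What cannot be interpreted is a stop or expansion driven by non-immune or liver events.

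**What to change.** For the study-level Part I endpoint and the >33% rule, state in Section 9.4.1 that events in the non-immune and liver bullets count unless attributed solely to disease progression or another non-treatment cause. Use the Section 8 scale, name the levels that count, and extend the scale to thoracic radiotherapy so that radiation toxicity is still captured. List all grade 3 or higher events alongside, regardless of cause. Give the lead-in's operating characteristics.

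Reconcile Section 9.4.1 with Section 8 and with the laboratory exceptions in Section 6.5.3.4. Section 4.1 uses the same term when referring to individual discontinuation, so confine the change to the study-level count; no individual rule is proposed here. Section 4.1 also starts the 13 weeks both at radiotherapy and at the first drug doses. These starts lie about 4 weeks apart and must be reconciled, because they determine which disease events fall inside the window.

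The cost is about a sentence in Section 9.4.1, one causality item on the adverse event form, and the reconciliation edits. The downside is that attribution needs judgement in a single-arm study; the all-cause listing keeps that judgement open to check.
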